3. INJECTED TUMOR RESPONSE RATE (ITR)

At a given visit, assess whether each injected tumor has achieved a PR or CR per RECIST 1.1. Count the total number of target (injected) tumors that achieve a PR or CR and divide by the total number of target tumors at that visit. This is the ITR. A PR is defined as a change $\geq 30\%$ in tumor volume, a CR is defined as having no visible tumor.

Note: for re-baselining retreated subjects that switch to a new cohort, the last assessment prior to the first retreatment is used as the baseline reference for determining PR.

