4.1.4. Long Term Follow up

Subjects who complete a full course of treatment including those who receive retreatment or who have discontinued treatment for any reason other than clinical or radiological progression will enter the Long Term Follow up period. During this time, subjects will be evaluated every 8 weeks for the first year and every 3 months thereafter. During this Long Term Follow up Period, if a subject progresses or receives an intervening anti-cancer therapy, the subject will then enter the Survival Follow up Period.

Subjects who discontinue treatment due to clinical or radiological progression or are Lost to Follow up or Withdraw Consent will not enter Long Term Follow up, but will enter survival follow up as outlined below.

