4.1.5. Survival Follow-up Period

Following completion of the treatment and long term follow-up, as applicable, all subjects will be followed for survival. After that initial assessment of all study subjects, any surviving subjects will have their survival status assessed approximately every 3 months by either a telephone or in-person contact until study completion or termination by the Sponsor. With the exception of noting the first use of subsequent anti-cancer therapies, no other data (e.g., subsequent therapies, performance status etc.) beyond survival will be collected during these calls/visits.

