7.6. Handling of Dropouts or Missing Data

Where individual data points are missing because of insufficient samples, dropouts, or other reasons, the data will be analyzed based on reduced denominators (e.g., using the response evaluable population). For survival analysis, dropouts without confirming events will be treated as censored.

All missing and partial start dates will be queried for a value. If a complete start date cannot be obtained, the following imputation rules apply in order to calculate duration of adverse event, concomitant medication use, or prior cancer history endpoints:

- Missing month and day
 - If the year of the incomplete start date is the same as the year of the date of study drug administration, then the missing month and day of the start date will be imputed to be the month and day of the start of study drug administration.
 - If the year of the incomplete start date is before the year of the date of study drug administration, December 31 will be assigned to the missing fields.
 - If the year of the incomplete start date is after the year of the date of study drug administration, January 1 will be assigned to the missing fields.

- Missing month only
 - If only the month is missing, the day will also be treated as missing, and both month and day will be replaced according to the above procedure.
- Missing day only
 - If the month and year of the incomplete start date are the same as the month and year of the date of study drug administration, the start date of study drug will be assigned to the missing field (i.e., AEs will be assumed treatment-emergent, and medications will be assumed concomitant).
 - If the month and year of the incomplete start date are before the month and year of the date of study drug administration, the last day of the month will be assigned to the missing field.
 - If the month and year of the incomplete start date are after the month and year of the date of study drug administration, the first day of the month will be assigned to the missing field.

If the stop date is complete and the imputed start date, when imputed as instructed above, is after the stop date, the start date will be imputed to equal the stop date.

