9. EFFICACY ANALYSES

Due to the method of action of the INT230-6 therapy observed over the course of the study, proper assessment utilizing RECIST or iRECIST was not possible. A response across all lesions using sum of diameters to assess efficacy over time using response criteria was not utilized. Thus, efficacy analyses will largely focus on the response of individual tumors (injected and bystander) as opposed to an overall tumor response, and any overall response will utilize the modified response criteria defined below.

Efficacy analyses will be conducted on the All Treated Population (ATP), the Response Evaluable Population (REP), and the Scan Evaluable Population (SEP). RECIST 1.1 assessments were not collected. Rather injected tumor response and non-injected tumor response utilizing some of the RECIST criteria were evaluated. Sponsor utilized RECIST principles with the injected and non-injected tumor measurements obtained. Efficacy will be determined based on a modified version of RECIST 1.1 criteria. Specifically, complete response (CR) and partial response (PR) will be defined for injected tumors followed per RECIST 1.1 utilizing target lesions. Progressive disease will be determined by clinical or radiological deterioration leading to the subject being taken off-treatment at the discretion of the investigator. Stable disease (SD) is defined as any adequate assessment not considered CR, PR, or progression. The appearance of a new lesion will not necessarily be considered progression and if possible will be assessed. Any post-baseline visit where a target lesion present at baseline was not assessed will result in a Not Evaluable (NE) assessment for that lesion. Data will be presented by treatment and, when indicated, by subgroups.

The primary efficacy parameter is the disease control rate (DCR), defined as the number of subjects obtaining a best overall response of either CR, PR, or SD as described above divided by the total number of subjects in the analysis population. The DCR will be presented with accompanying 95% exact binomial confidence intervals for each study part for the ATP population, REP, SEP, and by subgroup.

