9.1. Additional Efficacy Analysis

Additional efficacy parameters include the duration of response (DOR), the injected tumor response (ITR), the bystander tumor response (BTR), progression free survival (PFS), and overall survival (OS). These endpoints will be summarized by treatment (see section 7 for definition of each treatment) and subgroup. Other than 1 listing reporting bystander tumors' diameter that declined over time that declined (noted below), the bystander tumor response rate (BTR) analysis will be conducted separately from the SAP from collected radiographic data.

DOR is defined as the time from first tumor assessment of CR, PR, or SD to the time of progressive disease or death due to any cause. For responders with no death or progression, DOR will be censored on the last non-PD tumor assessment or follow-up call.

The median DOR as obtained from Kaplan-Meier methods will be presented by treatment and subgroup and will include the median, 25th percentile, 75th percentile, and a 2-sided point-wise 95% confidence interval.

ITR will be based on the target tumors at the baseline visit; tumors that become target during the study will also be included in the ITR calculation at the time they are treated. The ITR is defined as the ratio of CR + PR in injected tumors / total number of injected tumors. Thus, bystander or non-target lesions dosed at later dates are not included in calculations for ITR.

The ITR will be calculated based on the maximum likelihood estimator and summarized in tables. The estimate of ITR will be accompanied by 2-sided 95% exact binomial confidence intervals as determined by the Clopper-Pearson method and assessed at each study-specified timepoint where an assessment is performed.

The BTR will follow the same definition as the ITR for bystander tumors. Note that bystander tumors that are injected on study will be included in the ITR calculation.

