4. BYSTANDER TUMOR RESPONSE RATE (BTR)

Follow the method for ITR, instead using bystander tumors. Note that if a bystander tumor is injected on study, this tumor can no longer be considered bystander after the date of injection and will be included in the ITR calculation from that injection date visit onward. This can cause the denominator to be dynamic over visits.

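### By-visit ITR takes the target tumors at each visit as its denominator, so it can drift through attrition, and it departs from the protocol's baseline denominator

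*SAP*

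**What the plan says.** Three definitions of the ITR denominator are in force.

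- **SAP Appendix 1, item 3.** At a given visit, count the target tumors in CR or PR and "divide by the total number of target tumors at that visit". Item 4 defines BTR by reference: "Follow the method for ITR, instead using bystander tumors". It then says of bystanders injected on study: "This can cause the denominator to be dynamic over visits".
- **SAP 9.1.** "The ITR is defined as the ratio of CR + PR in injected tumors / total number of injected tumors". The same section plans an estimate with a 95% Clopper-Pearson interval at every scheduled assessment. It is also unclear about tumors injected later: one sentence brings them in from the time of treatment, another leaves out bystanders dosed at later dates, and a third puts injected bystanders back in.
- **Protocol 12.2.2.** Confirmed CR or PR, divided by the injected (or bystander) tumors identified at baseline. Protocol 12.2.1 nevertheless allows bystanders and new lesions that are later injected to enter ITR.

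On missing data, SAP 7.6 states that where points are missing through dropout or other causes "the data will be analyzed based on reduced denominators". SAP 9 gives a baseline target lesion left unmeasured at a post-baseline visit the status NE, but does not say whether an NE lesion stays in the ITR denominator.

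On who leaves, SAP 9 reads: "Progressive disease will be determined by clinical or radiological deterioration leading to the subject being taken off-treatment at the discretion of the investigator". Under SAP 4.1.4 such subjects "will not enter Long Term Follow up, but will enter survival follow up as outlined below". Under SAP 4.1.5, apart from the first subsequent anti-cancer therapy, no data "beyond survival will be collected during these calls/visits". Subjects who stop for most other reasons go on being scanned (protocol 5.3 and 12.1.4).

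SAP 13 lists no changes from the protocol's methods.

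**The concern.** Injected tumor response is a secondary endpoint for DEC, DEC2 and FEC, and bystander response is also secondary for FEC (SAP Table 2). SAP 9 says RECIST and iRECIST could not be applied properly and moves the weight of the efficacy analysis to individual tumors. ITR will therefore be read closely.

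The planned output is a series of rates over visits. If the tumors of subjects who progress leave the denominator, later rates describe only the tumors of subjects still being scanned. A rise along the series would look like deepening response when part or all of it could be a change in who is counted. The study is single-arm within each cohort, so no concurrent control would show the same drift and expose it.

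Separately, the reader of the study report could not tell which of the three denominators produced a given ITR, because SAP 13 says nothing has changed.

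**Working it through.** **Plan's own figure.** None: the documents state no ITR, BTR, tumor count or dropout rate. As a check on the interval routine only, 90% Clopper-Pearson limits at n = 16 came out at 5.3–41.7% for 3 responders, 9.0–48.4% for 4 and 13.2–54.8% for 5, matching SAP 5 to rounding.

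**Inputs.** The denominator rule is from Appendix 1 item 3, the dropout rule from 7.6 and the exit rules from 4.1.4, 4.1.5 and 9. All counts below are assumptions for illustration.

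**Formulas.** Let N be the injected tumors at the start, r those responding, and k the non-responding tumors whose subjects have left, with no new response.

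- By-visit rate = r / (N − k)
- Set-denominator rate = r / N

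For r > 0 and k > 0 the first exceeds the second.

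**1. Only non-responding tumors leave (N = 100).**

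| k lost | r = 30, by visit | r = 20, by visit |
|---|---|---|
| 0 | 30/100 = 30.0% | 20/100 = 20.0% |
| 10 | 30/90 = 33.3% | 20/90 = 22.2% |
| 20 | 30/80 = 37.5% | 20/80 = 25.0% |
| 30 | 30/70 = 42.9% | 20/70 = 28.6% |
| 40 | 30/60 = 50.0% | 20/60 = 33.3% |
| 50 | 30/50 = 60.0% | 20/50 = 40.0% |

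With r = 30 and k = 40, the by-visit 95% interval is 36.8–63.2%. On the set denominator the result stays at 30.0% (21.2–40.0%) at every row.

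**2. Some of the leavers respond (r = 30, N = 100, 40 tumors leave).** If a share s of the leavers are responders, the rate is (30 − 40s)/60.

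- s = 10%: 26/60 = 43.3%
- s = 20%: 22/60 = 36.7%
- s = 30%: 18/60 = 30.0%
- s = 50%: 10/60 = 16.7%

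The rate rises only if s is below the starting rate of 30%.

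**3. New injections enter (r = 30, 30 non-responding tumors leave, e non-responding tumors are newly injected).** The rate is 30/(70 + e).

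- e = 10: 30/80 = 37.5%
- e = 30: 30/100 = 30.0%
- e = 40: 30/110 = 27.3%

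**4. BTR without any dropout.** Take 60 bystanders, 6 responding. Moving 10, 20 or 30 non-responding bystanders to the injected group gives 6/50 = 12.0%, 6/40 = 15.0% or 6/30 = 20.0%, from 6/60 = 10.0%. This is the movement that Appendix 1 item 4 acknowledges.

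**5. Which remedy.** Take case 2 with s = 10%, so 4 responding tumors leave. By visit: 26/60 = 43.3%. Treating every tumor of a departed subject as non-responding: 26/100 = 26.0%, which erases four documented responses. Best response per tumor over the 100: 30/100 = 30.0%.

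**The case against.** - **A cumulative denominator is a possible reading.** SAP 9 says a target lesion never loses that status, and an unmeasured one is NE, so the tumors counted at a visit could include everything injected so far. This is fair, but a subject who has died or left has no visit at which NE could be assigned, the place of NE in the denominator is not stated, and 7.6 points to reduced denominators. The text at best leaves the matter open.
- **The direction is not fixed.** A reader might infer that ITR must rise as non-responding subjects leave. The documents do not support that. Exit is decided per subject and response per tumor: a subject can deteriorate clinically or through uninjected disease while injected tumors are in response. Cases 2 and 3 show the rate flat or falling. This stands and limits the claim.
- **SAP 9.1 and the Appendix do not flatly conflict.** Section 9.1 is itself assessed by timepoint, and the Appendix supplies programming detail. This largely stands. The clear departure is from protocol 12.2.2.
- **The sentence on a dynamic denominator is not an admission about dropout.** A reader might take it so. It follows from the rule on injected bystanders and concerns reclassification only. Attrition is simply not mentioned.
- **BTR is mostly outside the SAP.** SAP 9.1 places its analysis elsewhere, and Table 2 does the same for both rates in the monotherapy cohorts. What that analysis does cannot be seen, so BTR is secondary here. ITR in DEC, DEC2 and FEC carries no such exclusion.
- **ITR is descriptive.** No test rests on it, DCR divides by all subjects in the analysis population, and individual tumor assessments are listed. This limits the consequence. The table convention in SAP 7.1, however, speaks of subjects rather than tumors, so a shrinking tumor count need not be displayed.

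**Conclusion.** The concern holds in conditional form. By-visit ITR, as programmed in Appendix 1, is open to informative attrition: missing data shrink the denominator, and the subjects who stop for progression are among those whose tumor data end. An upward drift without new responses is the likelier result, because subjects taken off for progression can be expected to have fewer responding tumors. That expectation is a judgement. The documents fix neither size nor direction. On the assumed counts, a starting 30.0% could read anywhere from 16.7% to 60.0% with no tumor changing state.

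The departure from the protocol needs no assumption. Protocol 12.2.2 sets a baseline denominator with confirmed responses, Appendix 1 uses a by-visit denominator without mentioning confirmation, SAP 9.1 is not fully aligned with either, and SAP 13 reports no change. This should be corrected, chiefly for ITR in DEC, DEC2 and FEC. It does not touch the primary safety endpoint or the DCR denominator.

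**What to change.** 1. Make the main ITR for DEC, DEC2 and FEC the best response per tumor over one set denominator, stated once: either tumors identified at baseline, as in protocol 12.2.2, or all tumors ever injected. State whether confirmation is required, as the protocol has it.
2. Keep responses documented before a subject left. Count as non-responding any tumor with no evaluable post-injection assessment, whether NE or because the subject departed.
3. Show by-visit ITR as supportive only, with the numbers of subjects and tumors assessed at each visit.
4. Apply the same denominator rule to the BTR definition in Appendix 1 item 4 and to the separate BTR analysis.
5. Reconcile protocol 12.2.1 and 12.2.2 with SAP 9.1 and Appendix 1 items 3 and 4, including the sentences in 9.1 on tumors injected later, and record the change in SAP 13.

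Cost: SAP wording and minor recoding, with no new data. The headline rate will probably be lower than late by-visit rates. Best response per tumor does not show loss of response, which is a reason to keep the by-visit display alongside it.

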At baseline, lesions are classified as measurable or nonmeasurable per either RECIST 1.1 guidelines, depending on the cohort. Baseline measurable lesions are further classified as target (injected) or bystander (non-injected), while non-measurable lesions are classified as non-target (non-target lesions are not eligible for injection). A sum of diameters (SOD) (longest for extranodal lesions and shortest for lymph nodes) will be calculated for all target lesions. Tumor volume (for target tumors with three dimensions) will also be calculated using the modified

ellipsoid method or by longest diameter if specified in an particular protocol amendment. Bystander lesions will be recategorized as target lesions once injected, but target lesions will always remain target lesions.

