APPENDIX 1.

The following information provides additional programming instructions to define important variables that are not available in the main SAP text.

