5. PROGRESSION DEFINITION

Progression is defined as a patient who radiographically or clinically deteriorated as captured on any number of forms designating the patient is ending treatment or death. This includes the end of treatment form, end of maintenance form, follow-up form, and survival form. Note that typical RECIST 1.1 indications of progression such as an increase in sum of longest diameters of 20% or the presence of a new lesion are not considered progression for the purposes of PFS.

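### The injected tumor response rule carries the RECIST 1.1 label but sets partial response at an undirected 30% change in tumor volume, a switch that SAP section 9 does not list

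*SAP*

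**What the plan says.** Appendix 1 of the SAP describes itself as "additional programming instructions to define important variables that are not available in the main SAP text". Its item 3 (ITR) instructs the programmer, at each visit, to "assess whether each injected tumor has achieved a PR or CR per RECIST 1.1". The same paragraph then adds "A PR is defined as a change $\geq 30\%$ in tumor volume". Item 4 sends bystander tumors through the same method.

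Section 9 states that "Efficacy will be determined based on a modified version of RECIST 1.1 criteria". On response it says that "complete response (CR) and partial response (PR) will be defined for injected tumors followed per RECIST 1.1 utilizing target lesions", with no percentage. The changes it then spells out concern progression, stable disease, new lesions and lesions that were not assessed.

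On measurement, section 9 says: "A sum of diameters (SOD) (longest for extranodal lesions and shortest for lymph nodes) will be calculated for all target lesions". Volume comes next, as an additional calculation: "Tumor volume (for target tumors with three dimensions) will also be calculated using the modified" ellipsoid method, or from the longest diameter where an amendment says so. Section 9 does not tie volume to PR. Appendix 1, item 5, describes RECIST 1.1 in diameters too, citing "typical RECIST 1.1 indications of progression such as an increase in sum of longest diameters of 20" percent.

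Protocol 12.2.2 applies iRECIST response categories to tumors that have not been injected. SAP section 13 declares no changes from the protocol's methods.

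**The concern.** One paragraph names a criterion and then defines its key category on a different scale. Item 3 holds the only number for PR in the visible text, so a programmer would reasonably follow it. The resulting rate would carry the RECIST 1.1 name although it is not based on diameters.

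Volume falls roughly with the cube of diameter, so the same 30% means very different things on the two scales. The wording also asks for a change rather than a decrease. Read literally, a tumor whose volume grows by 30% would qualify.

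This matters because section 9 says the efficacy analyses will concentrate on individual tumors, and SAP Table 2 makes injected tumor response a secondary endpoint in DEC, DEC2 and FEC. A reader of the report could not tell from the visible text which metric lies behind the rate.

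**Working it through.** **1. Inputs.** The volume formula is longest × shortest × depth × 0.63 (Appendix 1, item 1). The PR threshold is 30% of volume (item 3). Tumors T-1 (4 × 3 × 3 cm) and T-2 (2 × 1 × 1.5 cm) come from the worked tumor burden example in Appendix 1. The documents print no diameter cut-off for PR, so the cut-offs below are assumptions and are shown as a range.

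**2. The SAP's own figure.** The four example volumes are 22.68 + 1.89 + 1.26 + 1.134 = 26.964 cc, as the SAP states. The formula is therefore read correctly.

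**3. Uniform shrinkage.** A volume fall v corresponds to a diameter fall of 1 − (1 − v)^(1/3). For v = 0.30 this is 1 − 0.7^(1/3) = 11.2%. In the other direction, a diameter fall c is a volume fall of 1 − (1 − c)³:

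| Assumed diameter cut-off | Equivalent volume fall | T-1 longest diameter at PR | T-2 longest diameter at PR |
|---|---|---|---|
| 10% | 27.1% | 3.6 cm | 1.8 cm |
| 20% | 48.8% | 3.2 cm | 1.6 cm |
| 30% | 65.7% | 2.8 cm | 1.4 cm |
| 50% | 87.5% | 2.0 cm | 1.0 cm |
| SAP rule, 30% volume | 30% | 4 × 0.7^(1/3) = 3.55 cm | 2 × 0.7^(1/3) = 1.78 cm |

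Under uniform shrinkage the volume rule is easier than any diameter cut-off above about 11%, and slightly harder than 10%. For T-2, PR needs a fall of only about 2.2 mm in longest diameter.

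**4. Non-uniform shrinkage.**
- Only the two shorter dimensions shrink: each must fall by 1 − 0.7^(1/2) = 16.3%, and the longest diameter does not move. T-1 at 4.0 × 2.5 × 2.5 cm is 0.63 × 25 = 15.75 cc, a fall of 6.93/22.68 = 30.6%. That is a volume PR with no change in longest diameter.
- Only the longest diameter shrinks: volume falls in the same proportion, so the rule needs a full 30% fall. T-1 at 2.8 × 3 × 3 cm is 15.876 cc, exactly −30%. Here the volume rule equals a 30% diameter cut-off and is stricter than a 20% one.

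**5. Why one volume method per tumor matters.** This step is conditional, because the SAP does not say that the one-dimension formulas of item 1 are used for ITR. For a longest diameter from 1.5 to 4 cm that formula is longest³/2, giving 64/2 = 32 cc for T-1 and 8/2 = 4 cc for T-2. If an unchanged tumor were computed that way at baseline and from three dimensions at follow-up, T-1 would read 22.68/32 − 1 = −29.1%, and T-2 would read 1.89/4 − 1 = −52.75%, a false PR.

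**6. Where it reaches.** Section 9 counts PR and stable disease alike in the disease control rate, so moving a subject between them changes nothing there. The primary safety endpoint does not use tumor size.

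**The case against.** The strongest reply is that the SAP is open about not applying standard RECIST. Section 9 says that proper assessment with RECIST or iRECIST was not possible, that response by sum of diameters across lesions was not used, and that only some of the criteria were applied. Appendix 1 then supplies the missing definition. This softens the point but does not remove it. Those statements concern response across lesions, while for PR in injected tumors section 9 still points to RECIST 1.1, and item 3 repeats that label beside the volume rule.

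Three further replies stand in part or in full:
- **Section 13.** A reader might infer that its nil entry is wrong for the ITR metric. The documents do not support that. Protocol 12.2.1 and 12.2.2 set no PR metric for injected tumors, so the SAP fills a gap there. The section 13 point holds only for bystander tumors under item 4, where the protocol names iRECIST categories. SAP 9.1 moves most of the bystander analysis outside the SAP.
- **Volume formula.** A reader might infer that the SAP gives none. It does, in section 9 and in Appendix 1, item 1. What is open is which method applies to ITR when dimensions are missing or an amendment changes the method.
- **Hidden evidence.** The public text shows only the last notes on a worked ITR example. The full example may show which metric was used, but it would not reconcile the written rule with its label.

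ITR is also descriptive, with no test or sample size resting on it.

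**Conclusion.** The point holds and should be fixed. Item 3 labels the assessment RECIST 1.1, defines PR by volume and gives no direction. Section 9 does not list the switch, and the SAP otherwise describes RECIST in diameters.

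Under uniform shrinkage the gap is 11.2% against an assumed 30% in diameter, or 30% against 65.7% in volume. The size depends on that assumed cut-off and on the shape of shrinkage. A reader might infer that the rule must inflate the response rate. The documents do not support so firm a statement: the rule is usually easier, but it equals a 30% cut-off when only the longest diameter shrinks and is slightly harder than a 10% cut-off under uniform shrinkage. Nor do they show whether volume was deliberate or a slip for diameter; the text needs correction in either case.

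ITR in DEC, DEC2 and FEC is affected, and the bystander rate where item 4 is applied. Whether monotherapy ITR lies inside this SAP (Table 2 against section 9.1) is a separate question. The disease control rate and the primary safety endpoint are untouched.

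**What to change.** In Appendix 1, items 3 and 4, replace the undirected wording with *decrease from baseline* and state one metric:

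1. keep the RECIST 1.1 label and use a diameter-based PR with its cut-off written out; or
2. keep the 30% volume rule under its own name, without the RECIST 1.1 label, and use the same one of the SAP's volume methods at baseline and follow-up for each tumor.

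Show the other metric as a supportive analysis. If volume is kept, add it to the modifications in section 9. In section 13, record the departure for bystander tumors from the iRECIST categories in protocol 12.2.2.

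The cost is a few sentences and a second run of ITR, and of the bystander rate where item 4 is used. Section 9.1 already lists diameters, depth, volume and percent change for each target and bystander tumor, so no new data are needed. The downside is that RECIST-labelled rates would probably be lower and two sets of rates would have to be explained. Option 2 leaves the volume figures as they are, provided one method was used throughout, and changes only their name.
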